D.1. Overview of Study Design. We propose a pilot study to test a 12-week video-enhanced nurse care management program for medically complex older Veterans with CI, delivered via telephone or through video visits. This study will test a 12-week intervention; in a larger RCT, we plan to continue the intervention for 12-months. Veterans aged 65 or older with Care Assessment Need (CAN) scores ≥ 75 will be contacted by phone and screened for CI using the TICS-m. Respondents with scores in the range of 20-29 (predictive of cognitive deficits in the mild range)²³ will be invited to participate in the study. Following informed consent and baseline data collection, participants will be randomized (1:1) to receive the intervention via *telephone* or through *video visits on iPads*. The program will consist of monthly telephone or video calls enabled by the Pexip Infinity application (version 12.2) on iPads, with the goal of providing structured information and support in two key areas: (1) care coordination (reduce workload) and (2) protecting cognitive health (build capacity). All subjects will participate in an outcome assessment call at week 14, consisting of survey items and a semi-structured interview. Study team will also conduct qualitative interviews with participants and their care partners after the 14 week assessment. These calls will be recorded and transcribed. At the beginning of each call, study staff will capture each patient's and care partner's assent to record the phone call. Study flow is illustrated in Figure 3. The study will enroll 40 dyads (Veteran participants and Care Partners).

D.2 Participant eligibility criteria.

D.2.a. Inclusion Criteria (Veteran). To be included in the study, patients must meet **all** of the following:

1. Receive primary care from a Durham VAMC affiliated primary care clinic (≥ 1 visit within the previous 12 months)
2. Age ≥ 65
3. CAN score ≥ 75
4. Participant must have a valid email address
5. Valid telephone number in the medical record
6. Identifies a friend or family member that we may contact for study participation as the Care Partner
7. TICS-m score 20-31

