D.5.a. Installing software for video calls. Participants who have their own iPad will be able to utilize it for the study. Patients who do not have access to an iPad will be loaned one for use during the study. All participants will be provided with detailed instructions for installing the Pexip Infinity application (version 12.2) application or have the application pre-installed on their device) and will have access to IT support over the telephone or in-person at the Durham VA with a study staff member and the facility telehealth coordinator if needed.

Consistent with current clinical policy for video visits, study staff will collect participant emails addresses to send an encrypted email to facility telehealth team for scheduling purposes. Emails addresses will not be stored in VA research databases. Research staff will not directly send or receive any emails to patients. All patients will participate in a test call with facility telehealth staff before scheduling their first study nurse call. We allot 2 weeks from the time of enrollment for the Pexip installation and completion of a test call. If the patient cannot complete the Pexip Infinity application (version 12.2) installation within this 2-week time frame (for any reason), the intervention will continue using telephone calls only. All patients in the Video-Enhanced Care Management Program (Arm 2) will be provided with an iPad cover with built-in stand and keyboard to make logging into Pexip easier and quality of video interaction better.

D.5.b. Technology solution for video calls. We have selected the Pexip Infinity application (version 12.2) for the video calls for several key reasons: 1) this technology meets all VA security standards and is currently in use

for in-home video telehealth encounters throughout VHA (FaceTime, Skype, etc. are not approved for use by VA clinicians); 2) facility telehealth coordinators can provide ongoing IT support (see Telehealth Coordinator letter of support); and 3) use of a tablet (iPad) enables mobility of the device to expand the applications of the video link to viewing aspects of the users home environment.

D.6. Measures and Data Sources

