Other Measures. We will collect information on patient socio-demographics, chronic medical conditions, self-rated health, health literacy, and sleep questions. We will review patient medical records to determine actions taken by the PCP as a result of the TICS-m score progress note (e.g. Geriatrics, Neurology referrals, Neuropsychology testing, scheduling a follow-up visit, etc.) and new diagnoses of CI or dementia.

D.7. Analyses

D.7.a. Aim 1: Examine the *feasibility* and *acceptability* of a 12-week care management program for medically complex Veterans with CI, delivered via telephone or through video visits. Feasibility will be examined by calculating overall rates of eligibility and enrollment, as well as rates of attrition, adherence to nurse calls or video visits, and interview completion. Clinical and personal characteristics associated with enrollment and study completion will be explored as well via contingency tables and regression analyses. Acceptability will be assessed using in-depth interviews with study participants (Veterans and Care Partners), primary care providers, and study staff (Section D.6.b.). We will conduct a formative evaluation of the intervention in order to elicit information about ways to enhance acceptability and effectiveness of the intervention in anticipation of testing it in a larger study.³⁸ Collecting qualitative data from relevant stakeholders including study participants, PCPs and study staff, will provide additional rich context for interpreting other quantitative study results.³⁹ Tasks and methods for each evaluation stage are described in the Appendix.

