D.7.b. Aim 2: Assess the *usability* and *perceived value* of video-enhanced care management, compared to telephone-based, among older Veterans with medical complexity and CI. We will administer the SUS at the 14-week outcome call to participants randomized to Arm 2 (video-enhanced.), care partners, and clinical staff. If any participants choose to withdraw from this Arm, we will administer this measure prior to withdrawal. We will examine overall sample mean, median, and distributions of scores according to established thresholds (e.g. >70 = excellent usability among those aged ≥65 years). Additionally, we will look at responses to individual items to see if certain items are more frequently endorsed (e.g. technical support item) to make refinements prior to a larger RCT. We will calculate means (or medians, as appropriate) and distributions of hospitalizations, ED visits, and patient-reported outcomes (PROMIS 29, PASE, MOS Social Support, PHQ-9, GAD-7) across time points, as well as changes between baseline and 14-week follow-up, as appropriate. Because of the small sample size, we will not conduct statistical testing. However, our descriptive analyses will allow us to evaluate whether there are clinically relevant differences in mean study outcomes between the two Arms (video-enhanced vs. telephone-based). Perceived value associated with each delivery method will be explored through questionnaires and in-depth interviews with study participants and study staff.

D.7.c. Sample size considerations. This is an exploratory pilot study that is not intended to test efficacy. While the sample size chosen must reflect the pragmatics of recruitment during a short enrollment period, we will have adequate sample size to provide meaningful confidence intervals for our estimates of feasibility, and comparisons between video and telephone delivery methods, and will have sufficient diversity of input on the intervention to plan refinements, if needed, prior to testing it in a larger RCT.

D.8. Dissemination and Implementation Plan

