The results of this pilot study will provide essential information about the feasibility, acceptability, usability, and perceived value of a care management program for medically complex Veterans with CI, delivered via telephone or through video visits on iPads. By using these preliminary data to refine study methods and optimize the intervention protocol prior to conducting a large RCT, we will enhance the efficiency and overall value of the subsequent trial. Specifically this pilot study addresses the important question of whether providing care management via video visits is feasible in this population, and if so, whether it offers added benefits, compared to telephone. To examine video visits, we will use the Pexip Infinity application which is currently approved and in preliminary clinical use in VHA, making rapid implementation highly feasible, if proven effective.

D.9. Project Management Plan

D.9.a. Summary of Research Team Experience. The research team is comprised of investigators from the HSR&D COIN for Health Services Research in Primary Care; the Geriatrics, Research, Education and Clinical Center (GRECC) at the Durham VA, the Duke University Center for the Study of Human Aging and Development and Alzheimer's Disease Research Center. We have assembled a multidisciplinary study team with a track record of productive collaboration, as well as relevant experience with all the methodology, data sources and analytic techniques described in the current proposal.

D.9.b. Timeline. We propose a **1 year study**. As illustrated below, we expect to begin enrollment in month 4 and complete data collection by month 10. The remainder of the study period will be dedicated to analysis of the data, dissemination of study results, and preparation of an IIR to test the intervention in an RCT.

	Month											
	1	2	3	4	5	6	7	8	9	10	11	12
Project Start Up												
Finalize IRB	X	X										
Develop study database and procedures	X	X	X	X								
Intervention Implementation												
Enroll patients				X	X	X	X					
Intervention and outcome assessments					X	X	X	X	X	X		
Data Analysis												
Planning for data analysis									X	X	X	X
Data analysis and reporting/ Prepare IIR											X	X

D.10. Data Management

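### D.7.c calls the sample adequate for confidence intervals but gives no width and plans no interval; a video-telephone difference in a feasibility rate would be known only to about ±19 to ±28 points

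*Combined protocol and SAP*

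**What the plan says.** D.1 fixes the size: "The study will enroll 40 dyads", randomized 1:1 to telephone or video, so about 20 per arm.

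D.7.a lists the feasibility measures for Aim 1: eligibility and enrollment, and then "rates of attrition, adherence to nurse calls or video visits, and interview completion". It also plans contingency tables and regressions on characteristics associated with enrollment and completion. It names no confidence interval.

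D.7.b describes means, medians and distributions by arm. It declines statistical testing because the sample is small, yet expects the descriptive results to show whether the arms differ by a clinically relevant amount. It names no interval either.

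D.7.c says the study is exploratory, is not meant to test efficacy, and was sized by what can be recruited in a short period. It then says "we will have adequate sample size to provide meaningful confidence intervals for our estimates of feasibility" and, in the same sentence, makes the same claim for comparing the two delivery methods.

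The closing section, Data Analysis and Statistical Considerations, says that no statistical analysis will be done because the sample is small.

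**The concern.** The only justification of sample size is a statement about confidence intervals, and three things are wrong with it. It cannot be checked, because it carries no width, confidence level or assumed rate. It has no counterpart in the analysis sections, where no interval is planned. It also conflicts with D.7.b and the closing section, which treat the same sample as too small to test or to analyze.

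D.8 gives the pilot a real question to answer before a large trial: "whether providing care management via video visits is feasible in this population", and if so whether it adds anything over telephone. Followed as written, the plan yields bare point estimates from about 20 dyads per arm, next to a statement that the sample is adequate for comparing the arms. Two similar observed rates could then be taken as evidence of no difference when the data leave a large gap open.

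**Working it through.** **The plan's own figure.** There is none to reproduce. The 40 dyads come without a derivation.

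**Inputs.** n = 40 overall and 20 per arm (D.1). The confidence level is not stated; I assume 95%, two-sided (z = 1.96). The expected rate is not stated; I show 50% to 95%. The nearest figures in the documents are 93% of video visits completed in a cited Parkinson's disease study (B.4.a) and 96% follow-up completion in the team's earlier telephone trial (B.7.a). Adherence is treated as a yes/no result per dyad, because D.7.a does not define its unit. The widths for a rate p also hold for 1 − p, so the 95% column covers 5% attrition.

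**Formulas.**
- Single rate, exact (Clopper-Pearson), x of n: lower limit = 2.5% point of Beta(x, n − x + 1); upper limit = 97.5% point of Beta(x + 1, n − x).
- Arm difference (Newcombe), with Wilson limits l and u for each arm: lower limit = d − √[(p₁ − l₁)² + (u₂ − p₂)²]; upper limit = d + √[(u₁ − p₁)² + (p₂ − l₂)²].

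**Results (95% limits, half-width in points).**

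| Rate | Overall, n = 40 | One arm, n = 20 | Arm difference, equal rates, 20 vs 20 |
|---|---|---|---|
| 95% | 83.1 to 99.4 (±8.2) | 75.1 to 99.9 (±12.4) | ±19.1 |
| 90% | 76.3 to 97.2 (±10.4) | 68.3 to 98.8 (±15.2) | ±21.4 |
| 80% | 64.4 to 90.9 (±13.3) | 56.3 to 94.3 (±19.0) | ±24.7 |
| 50% | 33.8 to 66.2 (±16.2) | 27.2 to 72.8 (±22.8) | ±28.4 |

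Example for the last column at 80%: the Wilson limits for 16/20 are 58.4 and 91.9, so the half-width is √[(80 − 58.4)² + (91.9 − 80)²] = √(466.6 + 141.6) = 24.7.

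Example with unequal rates: for 18/20 against 14/20 the observed gap is 20 points. The Wilson limits are 69.9 to 97.2 and 48.1 to 85.5. The lower limit is 20 − √(20.1² + 15.5²) = −5.4 and the upper limit is 20 + √(7.2² + 21.9²) = +43.1. An observed gap of 20 points would not exclude zero.

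**Rates with a larger denominator.** Eligibility and enrollment are computed on Veterans screened or contacted, not on 40. D.2.f expects 34-40% to screen positive, a figure given for the 20-29 score range although the current range is 20-31. Reaching 40 then needs at least 40/0.40 = 100 to 40/0.34 ≈ 118 Veterans screened, even if every positive enrolls. The half-width for the screen-positive share is 1.96 × √(0.40 × 0.60/100) = ±9.6 points, or 1.96 × √(0.34 × 0.66/118) = ±8.5 points.

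**The case against.** **No standard is set, so none is failed.** A reader might infer that the precision D.7.c promises is shown not to be delivered. The documents do not support that. They attach no target width and no feasibility threshold to the claim, and an overall interval such as 64-91% or 83-99% may be quite informative for an exploratory pilot. This objection stands for the overall rates.

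**The true rate may be high.** At 95%, near the documents' 93% and 96%, the intervals are narrower: ±8 overall and ±12 per arm. That is right, and it is why a range is shown. The arm difference is still ±19, and neither figure comes from Veterans with cognitive impairment using video.

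**The arm comparisons spelled out in D.7.b are mean outcomes and perceived value, not feasibility rates.** This is true, but D.7.c claims adequacy for comparing delivery methods without that limit. Mean outcomes do not rescue it: with 20 per arm the half-width is 2.024 × √(2/20) = 0.64 SD.

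**Repeated visits.** D.5.a says that if installation fails, "the intervention will continue using telephone calls only". A reader might infer that visit-level adherence intervals will be badly overconfident, because one failed installation removes all four video visits. No section plans a per-visit interval, the documents give no non-installation rate, and a contact moved to telephone may still count as adherence. No design effect or coverage figure can be derived from the documents.

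**No decision rests on the rates.** The plan has no rule that picks a delivery mode from them, and D.8 speaks of refining methods. That limits the harm to interpretation.

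**Conclusion.** The point holds as one of unsupported and inconsistent wording. For attrition, adherence and interview completion overall, adequacy is asserted without support rather than shown false: the half-width runs from about ±8 points (rate 95%) to ±16 (rate 50%). For comparisons of these rates between arms the claim is not tenable anywhere in that range. At best ±19 points and at worst ±28, two equal observed rates leave a gap of about 19 points or more open, and the plan itself calls the sample too small to test. The widths do not apply to eligibility and enrollment.

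The figures assume 95% two-sided intervals, 20 dyads per arm, equal rates in the two arms for the difference, and a yes/no measure per dyad.

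**What to change.** 1. In D.7.c, replace the adequacy sentence with the widths and the rates they assume, for example: with 40 dyads the 95% half-width for a feasibility rate is about ±8, ±10, ±13 and ±16 points overall at rates of 95%, 90%, 80% and 50%; ±12, ±15, ±19 and ±23 within an arm; and ±19, ±21, ±25 and ±28 for an arm difference with equal rates.
2. State that arm differences in feasibility rates are descriptive and that similar observed rates will not be read as no difference.
3. In D.7.a, commit to exact or Wilson 95% intervals for attrition, interview completion and adherence, with the dyad as the unit. Define adherence per dyad, including whether a video contact completed by telephone counts.
4. Compute eligibility and enrollment on Veterans screened or contacted, and name the denominator of each.
5. Amend the closing section so that it rules out hypothesis tests between arms but allows these intervals and the regressions in D.7.a.

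The cost is a change of protocol wording and a few intervals to report. No extra participants or data are needed. The stated precision will look less favorable.
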